APPENDIX 1: Definitions

1. Postoperative complications (24)

The primary outcome is postoperative infection of Clavien-Dindo grade II or greater within 30 days of randomisation. This is defined as one or more of the following infections:

- i. Superficial surgical site infection;
- ii. Deep surgical site infection;
- iii. Organ space surgical site infection;
- iv. Pneumonia;
- v. Urinary tract infection;
- vi. Laboratory confirmed blood stream infection;
- vii. Source uncertain; this is defined as an infection which is one or more of the above (i.e. i-vi), but it is unclear which.

Patients who die before day 30 without experiencing an infection will be counted as having 'no infection'. This is because death after a different type of complication will be related to a different biological mechanism. Patients who die before day 30 and have experienced an infection will be counted as having an infection. The date of infection is defined as the date a patient first receives treatment for that infection. In cases where there has been more than one infection, only the date of the first infection will be recorded. Infection must be of Clavien-Dindo grade II or greater, as follows:

Clavien-Dindo scale grading:

- Any deviation from the normal postoperative course without the need for pharmacological, surgical, endoscopic or radiological intervention. Antiemetics, anti-pyretics, diruetics, electrolytes or physiotherapy are not considered a deviation from the normal postoperative course.
- II. Requires pharmacological treatment with drugs (including blood transfusion or total parenteral nutrition) other than those excluded from grade I.
- III. Requires surgical, endoscopic or radiological intervention.
- IV. Life-threatening complication requiring critical care admission
- V. Death

Definitions of infections

Surgical site infection (superficial surgical site)

An infection at the surgical incision site which meets the following criteria:

- Involves only skin and sub-cutaneous tissue of the incision and
- The patient has at least one of the following:
 - purulent drainage from the superficial incision
 - organisms isolated from an aseptically obtained culture of fluid or tissue from the superficial incision
 - at least one of the following symptoms or signs of infection: pain or tenderness, localized swelling, redness, or heat, and superficial incision is deliberately opened by surgeon and is culture positive or not cultured. A culture-negative finding does not meet this criterion.
 - diagnosis of an incisional surgical site infection by a surgeon or attending physician

Surgical site infection (deep surgical site)

An infection at the surgical incision site which meets the following criteria:

- Involves deep soft tissues (e.g. fascial and muscle layers) of the incision and
- The patient has at least one of the following:
 - purulent drainage from the deep incision but not from the organ/space component of the surgical site
 - a deep incision spontaneously dehisces or is deliberately opened by a surgeon and is culture-positive or not cultured when the patient has at least one of the following symptoms or signs: fever (>38°C), or localized pain or tenderness. A culture-negative finding does not meet this criterion.
 - an abscess or other evidence of infection involving the deep incision is found on direct examination, during surgery, or by histopathologic or radiologic examination
 - diagnosis of an incisional surgical site infection by a surgeon or attending physician

Surgical site infection (organ/space)

An infection at the surgical incision site, excluding the fascia or muscle layers, which appears to be related to the surgical procedure and involves any part of the body, excluding the skin incision, fascia, or muscle layers, that is opened or manipulated during the operative procedure and the patient has at least one of the following:

- purulent drainage from a drain that is placed through a stab wound into the organ/space
- organisms isolated from an aseptically obtained culture of fluid or tissue in the organ/ space
- an abscess or other evidence of infection involving the organ/space that is found on direct examination, during reoperation, or by histopathologic or radiologic examination
- diagnosis of an organ/space surgical site infection by a surgeon or attending physician

Pneumonia

This is defined as two or more serial chest radiographs with at least one of the following (one radiograph is sufficient for patients with no underlying pulmonary or cardiac disease):

- a. new or progressive and persistent infiltrates
- b. consolidation
- c. cavitation

And at least one of the following:

- a. fever (>38°C) with no other recognized cause
- b. leucopenia (<4,000 white blood cells/mm³) or leucocytosis (>12,000 cells/mm³)
- c. for adults >70 years old, altered mental status with no other recognized cause

And at least two of the following:

- a. new onset of purulent sputum or change in character of sputum, or increased respiratory secretions, or increased suctioning requirements
- b. new onset or worsening cough, or dyspnoea, or tachypnoea
- c. rales or bronchial breath sounds
- d. worsening gas exchange (hypoxia, increased oxygen requirement, increased ventilator demand)

Urinary tract infection

A positive urine culture of $\geq 10^5$ colony forming units/mL with no more than two species of micro-organisms with at least one of the following symptoms or signs: fever (>38 °C), urgency, frequency, dysuria, supra-public tenderness, costo-vertebral angle pain or tenderness with no other recognised cause, identified within a 24-hour period.

Alternatively, the patient has an abscess or other evidence of infection seen on direct examination, during a surgical operation, or during a histopathologic examination with one of the following:

- a) purulent drainage from affected site;
- b) radiographic evidence of infection;
- c) physician diagnosis of infection of the kidney, ureter, bladder, urethra, or tissues surrounding the retroperitoneal or perinephric space;
- d) physician institutes antibiotic therapy for an infection of the kidney, ureter, bladder, urethra, or surrounding tissues.

Laboratory confirmed bloodstream infection

An infection which meets at least one of the following criteria but is not related to infection at another site:

- Patient has a recognised pathogen cultured from one or more blood cultures and the organism cultured from blood is not related to an infection at another site
- Patient has at least one of the following signs or symptoms: fever (>38°C), chills, or hypotension and at least one of the following:
 - a) common skin contaminant cultured from two or more blood cultures drawn on separate occasions
 - b) common skin contaminant cultured from at least one blood culture from a patient with an intravascular line, and the physician institutes antimicrobial therapy
 - c) positive blood antigen test

Infection, source uncertain

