7.4 Trial intervention

The trial intervention period will commence at the **start of general anaesthesia** and continue until **four hours after the completion of surgery** (maximum total duration: 24 hours).

Perioperative management for all patients

Care for all patients has been loosely defined to avoid extremes of clinical practice but also practice misalignment (11). All patients will receive standard measures to maintain oxygenation (SpO₂ \geq 94%), haemoglobin (>8 g/dl), core temperature (37 °C) and heart rate (<100 bpm). A fluid selected from the Standard Operating Procedure (SOP) for the trial intervention will be administered at 1ml/kg/hr to satisfy maintenance fluid requirements. Additional fluid will be administered at the discretion of the clinician guided by pulse rate, arterial pressure, urine output, core-peripheral temperature gradient, serum lactate and base excess. Mean arterial pressure will be maintained between 60 and 100 mmHg using an alpha adrenoceptor agonist or vasodilator as required. The trial interventions will commence with induction of anaesthesia and continue until four hours after the end of surgery. Post-operative analgesia will be provided at the discretion of the clinician by epidural infusion (bupivacaine and fentanyl), intrathecal opioids (fentanyl, morphine, diamorphine), wound catheter infusion (bupivacaine), patient-controlled analgesia system (morphine, fentanyl, oxycodone), oral analgesics (including morphine or oxycodone) or intra-venous infusion (morphine or fentanyl). If required, post-operative sedation will be provided with propofol or midazolam. The intervention period will last a maximum of 24 hours (although in most cases much less than this).

Intervention group

The intervention will commence from the induction of general anaesthesia and continue for four hours following surgery. Cardiac output and stroke volume will be measured by cardiac output monitor. Investigators may only use commercially available cardiac output monitoring equipment provided by Edwards Lifesciences in this trial. The specific details of the intervention are available in the SOP for the trial intervention. The manufacturers of the cardiac output monitors will provide this technology on loan to trial sites. No more than 500ml of intra-venous fluid will be administered prior to commencing cardiac output monitoring. In addition to the maintenance fluid and blood products described previously, patients will receive

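### Analgesics are missing from the Appendix 1 list of treatments that do not raise a complication to grade II, so an infection given only a new non-antipyretic analgesic counts, read literally, as a primary-outcome event

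*Protocol*

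**What the plan says.** Protocol section 5.2 restricts the primary outcome to infections of Clavien-Dindo grade II or greater, and Appendix 1 repeats this: "Infection must be of Clavien-Dindo grade II or greater, as follows". Appendix 1 then prints its own version of the scale.

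- Grade I: "Any deviation from the normal postoperative course without the need for pharmacological, surgical, endoscopic or radiological intervention".
- Exempt treatments, listed under grade I: "Antiemetics, anti-pyretics, diruetics, electrolytes or physiotherapy are not considered a deviation from the normal postoperative course".
- Grade II: "Requires pharmacological treatment with drugs (including blood transfusion or total parenteral nutrition) other than those excluded from grade I".

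The exempt list is closed. It gives no examples-only wording and no general clause, and nothing elsewhere in the protocol exempts analgesics.

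Section 7.4, under the management that applies to all patients in both arms, says: "Post-operative analgesia will be provided at the discretion of the clinician by epidural infusion", and goes on to name intrathecal, wound catheter, patient-controlled, oral and intravenous routes. Several of the named drugs are opioids.

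**The concern.** The exempt list exists to name treatments that belong to ordinary recovery and so should not raise a complication's grade. By the protocol's own account in section 7.4, analgesia is part of ordinary recovery for these patients. Leaving it off the list conflicts with the list's purpose.

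The grade II threshold separates infections that needed treatment from trivial ones. If pain relief alone can carry an infection over it, two assessors can score the same patient differently: one applies the printed text, the other disregards analgesics as a matter of habit. Outcomes are decided at each site, in several countries, and section 5.7 describes no central adjudication that would even this out. Any extra events that the intervention does not influence would also weaken the contrast between arms, in a trial planned at 80% power for its main target difference.

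**Working it through.** **Step 1. Can an infection meet its definition without an antimicrobial or a procedure?** Yes. In Appendix 1, a superficial or deep surgical site infection can rest on purulent drainage from the incision or on a diagnosis by a surgeon or attending physician. Neither route requires an antibiotic or an intervention.

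**Step 2. What grade does such an infection get if the only drug given for it is an analgesic?** Grade I is ruled out if a drug outside the exempt list was needed. Grade II is any needed drug outside that list. An opioid is not an antiemetic, antipyretic, diuretic or electrolyte. The literal result is grade II, and so a primary-outcome event.

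**Step 3. How narrow is the case?** All four of these must hold: the infection definition is met; no antimicrobial is given; no surgical, endoscopic or radiological intervention is made; and a new or increased analgesic that is not also an antipyretic is given because of the infection. The documents do not say how often this happens.

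**Step 4. Reproduce the planned sample size.** Inputs from section 8.1: 30% v 25%, 80% power, 5% type I error (taken as two-sided), 1:1 allocation. Using the pooled-variance formula without continuity correction:

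n per arm = [1.96 × √(2 × p̄ × (1 − p̄)) + 0.8416 × √(p1(1 − p1) + p2(1 − p2))]² / (p1 − p2)²

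With p̄ = 0.275, the two square roots are 0.6315 and 0.6305, and n = 1250.7, rounded up to 1251 per arm or 2502 in total. This matches the protocol. The second statement in section 8.1, 30% v 24%, gives 92.3% power against the stated 92%.

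**Step 5. Sensitivity to added events (assumption).** Suppose analgesic-only infections add x percentage points to each arm on top of 30% v 25%, unaffected by treatment. Power = Φ{[(p1 − p2)√n − 1.96 × √(2p̄(1 − p̄))] / √(p1(1 − p1) + p2(1 − p2))}, with n = 1251, so that (p1 − p2)√n = 0.05 × √1251 = 1.7685 throughout.

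| x (points) | Rates | Risk ratio | Power |
|---|---|---|---|
| 0 | 30% v 25% | 0.833 | 80.0% |
| 1 | 31% v 26% | 0.839 | 79.1% |
| 2 | 32% v 27% | 0.844 | 78.3% |
| 3 | 33% v 28% | 0.848 | 77.6% |
| 4 | 34% v 29% | 0.853 | 76.8% |

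The loss is 0.9 to 3.2 percentage points of power. The range of x is assumed, as is the absence of a treatment effect on these events.

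**The case against.** The strongest reply is that the literal reading seldom bites. Grade II speaks of treatment that is required, so routine background analgesia does not raise the grade of an infection that happens to be present. Drugs that are both analgesic and antipyretic can be read as already exempt. Infections treated with antibiotics or a procedure reach grade II or III anyway. Section 5.7 also has a site Principal Investigator, or a senior deputy, confirm or refute every infection call. All of this stands, and it makes the affected group small. It does not close the gap: new opioid treatment for a painful infected wound remains, the assessors work from drug charts with no rule for separating it from routine analgesia, and the person confirming the call applies the same printed text.

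A reader might infer more than the documents support, in five ways.

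- **Pain as a route into the outcome.** The definition of superficial surgical site infection lists "pain or tenderness, localized swelling, redness, or heat", but these signs count only when the surgeon has also deliberately opened the incision and it is culture-positive or not cultured. Pain alone never qualifies, and opening the wound arguably reaches grade III regardless of any analgesic.
- **The infection date.** Appendix 1 dates an infection from its first treatment. That is most naturally read as treatment of the infection, not of pain, and no analysis described in the protocol uses the date beyond the 30-day window.
- **The secondary outcomes.** Acute kidney injury and acute cardiac events use the same grade II threshold, but there is no worked case of an analgesic raising the grade of either.
- **A larger power loss.** If analgesic-only events lay within the planned 30% and were untouched by treatment, with the risk ratio of 0.833 applying to the rest, power would be 77.2% at 1 point and 71.0% at 3 points. The 3-point case needs 3/30 = 10% of control-arm events to be of this kind, and nothing in the protocol suggests that.
- **Bias between arms.** Sections 5.7 and 7.6 call for assessors who are unaware of allocation, so nothing here points to an effect in one direction.

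**Conclusion.** The point holds as a narrow error in the outcome definition. The printed grading rule counts, as a primary-outcome event, an infection whose only drug treatment is a new or increased non-antipyretic analgesic, and this conflicts with the protocol's own description of analgesia as part of every patient's care. It is a rule stated wrongly in the protocol, not a detail that could be left to the statistical analysis plan.

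The expected consequence is slight dilution and some inconsistency between sites. On the assumption of 1 to 4 extra points in each arm, power falls from 80.0% to between 79.1% and 76.8%. The true frequency is unknown and probably towards or below the low end of that range, given the four conditions that must coincide. Severity is low.

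**What to change.** Add 'analgesics' to the exempt treatments listed under grade I in Appendix 1, and carry the same wording into the assessor guidance.

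This is one word in the outcome definition, and it changes no patient's care. The cost is that a few minor events drop out of the count.

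The change should stop there. Requiring an antimicrobial before an infection can be grade II would redefine the primary endpoint, because the present grade II covers any non-exempt drug and expressly includes transfusion and parenteral nutrition. The omission of analgesics does not justify that.

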Acute episode of severe confusion or personality change which may result in hallucinations or delusional beliefs in the absence of a pre-existing diagnosis which may account for the clinical symptoms and signs.

Acute respiratory distress syndrome

Develops within one week of surgery; and Chest radiograph or computed tomography scan demonstrating bilateral opacities not fully explained by effusions, lobar/lung collapse or nodules; and Respiratory failure not fully explained by cardiac failure or fluid overload; and Oxygenation meets one of the following criteria (note severity still graded according to Clavien-Dindo system):

- a. Mild: PaO₂:FiO₂ between 200 and 300 mmHg with PEEP or CPAP \geq 5 cmH₂O^c
- b. Moderate: PaO_2 :FiO₂ between 100 and 200 mmHg with PEEP \geq 5 cmH₂O
- c. Severe: PaO_2 : FiO₂ ≤100 mmHg with PEEP ≥5 cmH₂O

Anaphylaxis

Severe, life-threatening, generalized or systemic hypersensitivity reaction.

Anastomotic breakdown

Leak of luminal contents from a surgical connection between two hollow viscera. The luminal contents may emerge either through the wound or at the drain site, or they may collect near the anastomosis, causing fever, abscess, septicaemia, metabolic disturbance and/or multiple-organ failure. The escape of luminal contents from the site of the anastomosis into an adjacent localised area, detected by imaging, in the absence of clinical symptoms and signs should be recorded as a sub-clinical leak.

Bowel infarction

Clinical diagnosis demonstrated at laparotomy.

Gastrointestinal bleed

Gastrointestinal bleed is defined as unambiguous clinical or endoscopic evidence of blood in the gastrointestinal tract. Upper gastrointestinal bleeding (or haemorrhage) is that originating proximal to the ligament of Treitz, in practice from the oesophagus,

stomach and duodenum. Lower gastrointestinal bleeding is that originating from the small bowel and colon.

Multi-organ dysfunction syndrome

A life threatening but potentially reversible physiologic derangement involving failure of two or more organ systems not involved in the primary underlying disease process.

Paralytic ileus

Failure to tolerate solid food or defecate for three or more days after surgery.

Perforated viscus

Clinical diagnosis demonstrated at laparotomy or confirmed by contrast enhanced radiograph or CT scan. For example perforated bowel, gall bladder etc.

Other postoperative haemorrhage (not gastrointestinal bleed)

Blood loss within 72 hours after the start of surgery which would normally result in transfusion of blood.

Pulmonary embolism

A new blood clot or thrombus within the pulmonary arterial system. Appropriate diagnostic tests include scintigraphy and CT angiography. Plasma D-dimer measurement is not recommended as a diagnostic test in the first three weeks following surgery.

Stroke

An embolic, thrombotic, or haemorrhagic cerebral event with persistent residual motor, sensory, or cognitive dysfunction (e.g. hemiplegia, hemiparesis, aphasia, sensory deficit, impaired memory).

Other definitions

1. Preoperative immunosuppressive treatment

Preoperative steroids: Regular administration of an oral or parenteral corticosteroid medication (e.g. Prednisone, Decadron) ending within 30 days prior to surgery for a chronic medical condition (e.g. COPD, asthma, rheumatoid arthritis, inflammatory bowel disease). Topical corticosteroids applied to the skin, or corticosteroids

administered rectally or by inhalation are not included. This does not include short course steroids of a duration of 10 days or less.

Preoperative chemotherapy for malignancy: Any chemotherapy treatment for cancer ending within 30 days prior to surgery. Chemotherapy includes, but is not restricted to oral and parenteral treatment with chemotherapeutic agents for malignancies such as colon, breast, lung, and gastrointestinal solid tumours as well as lymphatic and hematopoietic malignancies such as lymphomas, leukaemia, and multiple myeloma. This does not include treatment consisting solely of hormonal therapy (25).

Other immunosuppressive treatment: any other immunosuppressive treatment given by the oral or parenteral route for 10 days or longer ending within 30 days prior to surgery, for chronic inflammatory or auto-immune conditions or transplant. This may include cytostatics (e.g. cyclophosphamide, methotrexate, azathioprine), monoclonal or polyclonal antibodies, calcineurin inhibitors (e.g. cyclosporin, tacrolimus, sirolimus) or others (e.g. mycophenolate, TNF-binding proteins). This does not include drugs administered by the topical, inhaled or rectal route.

2. Level of care after surgery

The level of care should be defined according to the care the patient received rather than the location. For example, a patient receiving level 2 care in a level 3 area should be recorded as receiving level 2 care.

- 1. Critical care level 3: includes advanced organ support e.g. invasive ventilation, renal replacement therapy.
- 2. Critical care level 2: may include advanced cardiorespiratory monitoring (e.g. invasive arterial / central venous monitoring) and basic organ support (e.g. non-invasive ventilation, inotropic/vasoactive drug administration).
- 3. Post-anaesthetic care unit: care within a designated area for the patients in the immediate recovery from anaesthesia. May deliver care at levels 1 to 3.
- 4. Surgical ward (level 0/1): normal ward care without level 2 or 3 capabilities.
